11.1.10 Adverse Events Leading to Dose Reduction of IMP

Adverse events leading to dose reduction of idalopirdine in the open label treatment period will be listed.

Adverse events leading to dose reduction of idalopirdine in the open label treatment period will be summarised by preferred term.

11.1.11 Adverse Events of Special Interest

The following standardized MedDRA queries (SMQ) will be summarised in total and by preferred term:

- Convulsions (narrow scope)
- Drug-related hepatic disorders -comprehensive search
- Haemorrhages (broad scope)

11.2 General Methodology for Other Safety Data

The denominators for the summaries of a given variable will be based on the number of patients with non-missing values at a given visit or during the assessment period.

Descriptive statistics for the safety variables in the open label treatment period, absolute values changes from both Baseline I and Baseline II, will be presented by visit and the last post-baseline assessment in the treatment period.

For the open-label treatment period with memantine, summaries will be presented for absolute values and change from Baseline III by visit and last assessment in the treatment period.

The number and percentage of patients with at least one PCS value at any post-Baseline II assessment in the open-label treatment period will be summarised by variable. The number and percentage of patients with at least one PCS value at any post-Baseline III assessment in the open-label treatment period with memantine will be summarised by variable . All available assessments will be included in the evaluation of PCS values (scheduled, reassessments, and unscheduled). For tests where PCS is defined as a change, the summaries will be prepared both for PCS compared to baseline I and baseline II for the open label treatment period.

For patients with post-baseline II PCS values (compared to baseline II) in the open-label treatment period, listings will be provided including all available values for the variable, with

LU Study Number: 14861B Trial Site Number: Study Level Pluto ID: CLI 00933680

Page 18 of 48

flagging of PCS values and out-of-reference-range values. The corresponding listings will be prepared for the open label treatment period with memantine.

All adverse events for patients with post-baseline II PCS value (compared to baseline II) in the open-label treatment periods will be listed by lead-in treatment group and patient screening number and include the PCS value; investigator term and preferred term for the adverse event; and intensity, seriousness, causality, action taken, outcome, start date, and duration of the adverse event; and days since first dose of IMP at the time of onset of the adverse event. The PCS value will be listed next to any adverse events occurring in the same visit window; the PCS values and adverse events will be listed in chronological order according to assessment date and the start date of the adverse event. The corresponding listings will be presented for the open-label treatment period with memantine.

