5.3 Selection Criteria

Patient selection is based on the inclusion and exclusion criteria listed below.

Patients who meet each of the inclusion criteria at the Baseline II Visit and none of the exclusion criteria at the Baseline II Visit are eligible to participate in this study.

Open-label treatment period (initial 28-week period):

Inclusion Criteria

- 1. The patient has completed Visit 7 (Completion Visit) in the lead-in study.
- 2. The patient's sight and hearing (hearing aid permissible) are, in the investigator's judgement, sufficient for compliance with the study procedures.
- 3. The patient (and/or if applicable the legal representative if different from the responsible caregiver) and the responsible caregiver are able to read and understand the *Informed Consent Form*.
- 4. The patient (and/or if applicable the legal representative if different from the responsible caregiver) and the responsible caregiver have signed the *Informed Consent Form*.
- 5. The patient is willing and able to attend study appointments within the specified time windows.
- 6. The patient has a knowledgeable and reliable caregiver who will accompany the patient to all clinic visits during the study.
- 7. The patient, if a man, must:
 - use two methods of contraception in combination if his female partner is of childbearing potential; this combination of contraceptive methods must be used from the Baseline II Visit to ≥1 month after the last dose of IMP, OR
 - have been surgically sterilised prior to the Completion Visit in the lead-in study.

Exclusion Criteria

- 1. The patient has experienced seizures before Completion Visit in the lead-in study.
- 2. The patient has evidence of clinically significant disease including but not limited to pulmonary, gastrointestinal, renal, hepatic, endocrine or cardiovascular system disease or metabolic disturbance (patients with controlled diabetes, or patients with controlled hypertension, or right bundle branch block, complete or partial, may be included in the study). Patients with pacemakers are eligible provided that they follow a routine check-up with their doctor and are considered stable. As specified in the donepezil *summary of product characteristics (SmPC)* special precaution is needed for patients with asthma, obstructive pulmonary disease, bradycardia, or difficulty in passing urine.

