- 3. The patient takes or has taken disallowed recent or concomitant medication (specified in Appendix II) or it is anticipated that the patient will require treatment with at least one of the disallowed concomitant medications during the study.
- 4. The patient's donepezil treatment is likely to be interrupted or discontinued during the study.
- 5. The patient is receiving therapy with another AChEI or memantine.
- 6. The patient has clinically significant abnormal vital signs at the Completion Visit in the lead-in study considered a potential safety risk by the Investigator.
- 7. The patient has a moderate or severe on-going adverse event from the lead-in study considered a potential safety risk by the investigator.
- 8. The patient has been tested positive for hepatitis B surface antigen (HBsAg), or hepatitis C virus/antibodies (anti-HCV), AND had abnormal ALT, AST or bilirubin in the lead-in study.
- 9. The patient has been tested positive for hepatitis B surface antigen (HBsAg), or hepatitis C virus/antibodies (anti-HCV) for the first time within the last 6 months prior to the Completion Visit in the lead-in study.
- 10. The patient has one or more clinical laboratory test values outside the reference range, based on the latest blood and urine sample results, available at the Completion Visit in the lead-in study, that are of potential risk to the patient's safety, or the patient has according to the latest available blood sample:
 - a serum creatinine value >1.5 times the upper limit of the reference range, or
 - a serum total bilirubin value >1.5 times the upper limit of the reference range, or
 - a serum alanine aminotransferase (ALT) or aspartate aminotransferase (AST) value >1.5 times the upper limit of the reference range.
- 11. The patient has, based on the latest ECG results, available at the Completion Visit in the lead-in study:
 - an abnormal ECG that is, in the investigator's opinion, clinically significant, or
 - a heart rate <45 beats per minute, or
 - a PR interval >280 ms, or
 - a QRS interval >150 ms, or
 - a QTcF interval >480 ms (based on the Fridericia correction where $QTcF = QT/RR_{0.33}$)

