Appendix IV PCS Criteria

LU Study Number: 14861B Trial Site Number: Study Level Pluto ID: CLI_00933680

PCS Criteria

Table 1 PCS Criteria for Clinical Safety Laboratory Tests

CDISC term	Test (units)	PCS Low	PCS High
Liver			
AST	S-aspartate aminotransferase (IU/L)		$\geq 3 \times ULN$
ALT	S-alanine aminotransferase (IU/L)		\geq 3 × ULN
BILI	S-bilirubin (μmol/L)		≥ 34
BILDIR	S-direct bilirubin (µmol/L)		≥ 12
ALP	S-alkaline phosphatase (IU/L)		$\geq 3 \times ULN$
GGT	S-gamma glutamyl transferase (IU/L)		≥ 200
Kidney			
CREAT	S-creatinine (µmol/L)		$\geq 1.5 \times ULN$
BUN	B-urea nitrogen (mmol/L)		≥ 11
Electrolytes			
SODIUM	S-sodium (mmol/L)	≤ 125	≥ 155
K	S-potassium (mmol/L)	≤ 3.0	≥ 6.0
CA	S-calcium (mmol/L)	≤ 1.8	≥ 3.0
BICARB	S-bicarbonate (mmol/L)	≤ 12	≥ 38
Endocrine/Meta	bolic		
GLUC	Serum glucose (mmol/L)	≤ 3.9	≥ 11.1
GLUC	Serum glucose, fasting (mmol/L)	≤ 3.5	≥ 7.0
TSH	S-thyrotropin (mIU/L)	≤ 0.3	≥ 5.5
ALB	Albumin (g/L)	≤ 27	
Lipids			
CHOL	S-cholesterol (mmol/L)		≥ 7.8
CHOL	S-Cholesterol, fasting (mmol/L)		≥ 6.2
TRIG	Triglycerides (mmol/L)		≥ 5.65
TRIG	Triglycerides, fasting (mmol/L)		≥ 4.2
Haematology/Co	pagulation		
INR	P-INR (Prothrombin ratio)		≥ 2.0
PLAT	B-thrombocytes platelet count (×10E9/L)	≤ 75	≥ 600
HGB	B-haemoglobin (g/dL)	≤ 9.5 (women) ≤ 11.5 (men)	≥ 16.5 (women) ≥ 18.5 (men)
RBC	B-erythrocytes (×10E12/L)	≤ 3.5 (women) ≤ 3.8 (men)	\geq 6.0 (women) \geq 7.0 (men)
WBC	B-Leukocytes (×10E9/L)	\leq 2.8	≥ 16
NEUTLE	B-Neutrophils/leukocytes (%)	≤ 20	≥ 85
EOSLE	B-eosinophils/leukocytes (%)		≥ 10

Page 47 of 48

LU Study Number: 14861B Pluto ID: CLI_00933680

Status: Final

Version: 1.0

CDISC term	Test (units)	PCS Low	PCS High
BASOLE	B-basophils/leukocytes (%)		≥ 10
LYMLE	B-Lymphocytes/leukocytes (%)	≤ 10	≥ 75
MONOLE	B-Monocytes /leukocytes (%)		≥ 15
Infection			
CRP	S-C-reactive protein (mg/L)		≥ 25
Urine			
GLUC	U-Glucose		Increase≥2
KETONES	U-Ketones		Increase≥2
OCCBLD	U-Occult Blood		Increase≥2

Table 2 PCS Criteria for Vital Signs and Weight

CDISC term	Variable (units)	PCS Criterion Low	PCS Criterion High
WEIGHT	Weight (kg)	Decrease ≥ 7%	Increase ≥ 7%
BMI	Body mass index (kg/m2)	Decrease $\geq 7\%$	Increase $\geq 7\%$
DIABP	Supine diastolic blood pressure (mmHg)	\leq 50 and decrease \geq 15	≥ 105 and increase ≥ 15
SYSBP	Supine systolic blood pressure (mmHg)	\leq 90 and decrease \geq 20	≥ 180 and increase ≥ 20
PULSE	Pulse rate supine/sitting/unknown (bpm)	\leq 50 and decrease \geq 15	\geq 120 and increase \geq 15

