Table 3 PCS Criteria for ECG Parameters

CDISC term	Parameter (units)	PCS Criterion Low	PCS Criterion High
Absolute Time Int	erval		
PRMEAN	PR interval (msec)		≥ 260
QRSDUR	QRS interval (msec)		≥ 150
QTMEAN	QT interval (msec)		≥ 500
Derived Time Inte	rval		
QTcB	QTcB interval (msec)	< 300	> 500 or increase > 60
QTcF	QTcF interval (msec)	< 300	> 500 or increase > 60
HRMEAN	ECG Mean heart rate (beats/min)	\leq 50 and decrease \geq 15	\geq 120 and increase \geq 15

Trial Site Number: Study Level

Version: 1.0

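### For potentially clinically significant (PCS) criteria that are absolute limits, the planned percentages mix abnormalities already present at baseline with new ones

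*SAP*

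**What the plan says.** SAP section 11.2 defines the summary for the open-label period as "The number and percentage of patients with at least one PCS value at any post-Baseline II assessment", by variable, with a parallel rule after Baseline III for the substudy. Scheduled, repeat and unscheduled values all count. On denominators it says: "The denominators for the summaries of a given variable will be based on the number of patients with non-missing values at a given visit"; for summaries over a whole period, the count of non-missing values is taken over that period. Neither sentence refers to PCS status at baseline, and the SAP plans no shift table and no PCS table by baseline status.

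The same section treats one class of criteria differently: "For tests where PCS is defined as a change, the summaries will be prepared both for PCS compared to baseline I and baseline II". For patients with PCS values, "listings will be provided including all available values for the variable, with" flags on PCS and out-of-range results. Absolute values and changes from Baselines I and II (Baseline III in the substudy) are also summarised by visit.

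Protocol section 5.3 excludes patients with "a PR interval >280 ms, or" other listed ECG findings, and allows a PR of 250-280 ms after discussion with the sponsor medical expert. It also admits "patients with controlled diabetes, or patients with controlled hypertension, or right bundle branch block". SAP Appendix IV sets the PCS limit for PR at 260 ms or more, and for non-fasting glucose at 11.1 mmol/L or more.

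**The concern.** Under an absolute limit, a patient beyond it at Baseline II who does not change is a counted case, the same as a patient who crosses it during treatment. The SAP avoids this for adverse events: section 11.1.4 leaves events already present at Baseline II that do not worsen to the lead-in report. It avoids it for change-defined PCS criteria by naming the reference baselines. Only the absolute criteria have no baseline reference.

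Safety is the primary objective and every patient receives idalopirdine, so there is no concurrent control against which stable background abnormality would cancel out. SAP section 5 splits the open-label tables by lead-in treatment group. Former placebo patients are newly exposed, while former idalopirdine patients may bring abnormalities from the lead-in, and the planned percentage cannot tell these situations apart. Protocol section 3.2 presents the substudy as a within-patient comparison before and after memantine is added; a count that ignores Baseline III does not use that comparison.

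**Working it through.** The plan states no figure for PCS rates, so there is none to reproduce. The check has three steps.

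**1. Which criteria are affected.** Rows in SAP Appendix IV, Tables 1-3:

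- Absolute only: 31 blood tests + PR, QRS and QT = 34.
- Change required: 3 urine tests + 5 vital-sign and weight rows + ECG heart rate = 9.
- Mixed: QTcB and QTcF = 2.
- Total: 34 + 9 + 2 = 45.

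These are rows in the tables, not analysed variables. Some rows, such as thyrotropin and fasting glucose, have no counterpart in protocol Panel 5.

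**2. Can a PCS value enter?** Entry limits (protocol section 5.3) against PCS limits:

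| Variable | Excluded at entry | PCS | Overlap |
|---|---|---|---|
| PR | >280 ms | ≥260 ms | Yes, 260-280 ms |
| Glucose, GGT, BUN, CRP, lipids, blood counts | No numeric limit; investigator's safety-risk judgement | Fixed limits | Possible |
| QRS | >150 ms | ≥150 ms | Only at 150 ms |
| Creatinine | >1.5×ULN | ≥1.5×ULN | Only at 1.5×ULN |
| Bilirubin | >1.5×ULN | ≥34 µmol/L | Only if ULN ≥ 34/1.5 = 22.7 µmol/L (ULN not given) |
| ALT/AST | >1.5×ULN (substudy >2×ULN) | ≥3×ULN | No |
| QTcF, absolute upper limit | >480 ms | >500 ms | No |

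The last two rows hold for the sample used for eligibility. Protocol section 8.2 uses the results available at Visit 7, so the Visit 7 sample that becomes Baseline II could still be higher.

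**3. Illustration of size.** Let b be the share already PCS at baseline, s the chance that such a patient has at least one later PCS value, and i the new-onset rate among the rest. All three are assumptions.

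Planned percentage = b·s + (1 − b)·i

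Share of counted patients who were already PCS = b·s / planned percentage

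| b | s | Planned, i = 1% (share) | Planned, i = 2% (share) |
|---|---|---|---|
| 0.5% | 50% | 1.25% (20%) | 2.24% (11%) |
| 0.5% | 100% | 1.50% (33%) | 2.49% (20%) |
| 2% | 50% | 1.98% (51%) | 2.96% (34%) |
| 2% | 100% | 2.98% (67%) | 3.96% (51%) |
| 5% | 50% | 3.45% (72%) | 4.40% (57%) |
| 5% | 100% | 5.95% (84%) | 6.90% (72%) |

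At i = 2% the extremes are 0.005 × 0.5 + 0.995 × 0.02 = 2.24% and 0.05 × 1 + 0.95 × 0.02 = 6.90%. With about 100 patients in the substudy, each carried-over case adds about one percentage point.

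**The case against.** The case for leaving the plan alone has substance.

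- The protocol (section 16.9.2) promises only that PCS values will be flagged and summarised, and the SAP does that. No commitment is broken, and counting every PCS value errs towards over-reporting.
- Clinically significant laboratory, vital-sign and ECG abnormalities must also be recorded as adverse events (protocol sections 9.4.2, 9.4.3 and 9.4.5), where the start-or-worsen rule applies. PCS percentages are therefore one safety output among several.
- The listings show all available values, and change-from-baseline summaries are planned, so pre-existing cases can be identified one by one.
- Entry is not open: any out-of-range laboratory value judged a safety risk excludes the patient, and a PR of 250-280 ms needs prior discussion.

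All of this stands, and it limits the point. It does not remove it, because a listing does not correct a summary percentage and a judgement clause does not rule out stable PCS values at entry.

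A reader might infer more than the documents support:

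- That all PCS summaries ignore baseline. Nine rows require a change, as does one part of QTcB and QTcF.
- That the leading liver and QT counts are contaminated by permitted entry values. For ALT/AST and QTcF >500 ms the entry limits are stricter than the PCS limits.
- That new abnormalities are hidden from the report as a whole. Only the summary percentages combine old and new.

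Conversely, a reader might take the reference to comparison with Baseline II in the PCS listings as an emergence rule. It governs listings rather than counts, and it has no defined meaning for an absolute limit.

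**Conclusion.** The point holds for absolute-limit criteria: 34 of 45 rows, plus the absolute part of QTcB and QTcF. For these, the planned percentages do not separate abnormalities present at baseline from those that appear later. PR at 260-280 ms is the documented case of a permitted entry value that is itself PCS. For glucose, GGT, BUN, CRP, lipids and blood counts it is possible, since no numeric entry limit applies.

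The size cannot be derived from the documents. The range of 2.2-6.9% against a 2% new-onset rate is an illustration resting entirely on the assumed prevalence and persistence; at low prevalence the distortion is small. This is a reporting weakness in an uncontrolled safety study rather than an error that invalidates the tables. It is still worth correcting, because the data are already collected and these percentages will be read without a control group.

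**What to change.** In SAP section 11.2, keep the planned all-patients count. For absolute criteria, including the absolute part of QTcB and QTcF, add the count and percentage of patients with a post-baseline PCS value split by PCS status at baseline (not PCS, PCS, missing), or a shift table. Do this against both Baseline I and Baseline II for the open-label period, by lead-in treatment group, and against Baseline III for the substudy.

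Do not replace the planned count with one restricted to patients who are not PCS at Baseline II. That visit follows 24 weeks of lead-in treatment. Taking the three equal arms per study implied by the sample-size formula, (2×310 + 2×280)/(3×310 + 3×280) = 1180/1770, about two thirds of randomised patients were assigned idalopirdine in the lead-in. Such a filter would drop abnormalities that arose on idalopirdine and persist, which is the wrong direction for a long-term safety objective. The Baseline I split keeps them visible.

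The cost is a few sentences of SAP text, some programming on data already held, extra table rows, and denominators that vary by variable. No entry limit or PCS limit needs to change.

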11.3 Clinical Safety Laboratory Test Data

11.3.1 Data Presentation

The PCS criteria for the clinical safety laboratory tests are in Table 1.

All the clinical safety laboratory test values will be presented in conventional and/or Système International (SI) units.

The summary statistics for GGT, ALT, AST, ALP, Bilirubin, and eosinophils will be presented in a separate tables, including worst (highest) post-Baseline II assessment during the open-label treatment period or post-Baseline III assessment during the open-label treatment period with memantine. All available assessments will be included in the evaluation of the worst assessment.

Graphical presentations of gamma glutamyl transferase (GGT), alanine aminotransferase (ALT), aspartate aminotransferase (AST), alkaline phosphatase (ALP), and bilirubin (BILI) are described Panel 3 (further graphical presentations of ALT, AST, ALP, and BILI will be done in the evaluation of drug-induced liver injury).

LU Study Number: 14861B Pluto ID: CLI 00933680

Status: Final

Trial Site Number: Study Level

Version: 1.0

Panel 3 Graphical Presentations for the Liver Function Tests

Laboratory Test	Measure	Patient Selection	Line Plot			
Open-label treatm	Open-label treatment period					
GGT	Absolute measure	Patients with a post-Baseline II value of GGT ≥200	$\sqrt{}$			
ALT	Absolute measure	Patients with a post-Baseline II value out of upper reference range for ALT	$\sqrt{}$			
AST	Absolute measure	Patients with a post-Baseline II value out of upper reference range for AST	$\sqrt{}$			
ALP	Absolute measure	Patients with a post-Baseline II value out of upper reference range for ALP	$\sqrt{}$			
BILI	Absolute measure	Patients with a post-Baseline II value out of upper reference range for BILI	$\sqrt{}$			
Open-label treatm	ent period with men	nantine				
GGT	Absolute measure	Patients with a post-Baseline III value of GGT≥200	$\sqrt{}$			
ALT	Absolute measure	Patients with a post-Baseline III value out of upper reference range for ALT	$\sqrt{}$			
AST	Absolute measure	Patients with a post-Baseline III value out of upper reference range for AST	$\sqrt{}$			
ALP	Absolute measure	Patients with a post-Baseline III value out of upper reference range for AP	$\sqrt{}$			
BILI	Absolute measure	Patients with a post-Baseline III value out of upper reference range for BILI	$\sqrt{}$			

11.3.2 Urinalysis

For tests based on urine dipsticks, the results are categorical, and the number and percentage of patients will be summarised for each test by visit week and last assessment in each treatment period.

11.3.3 Evaluation of Potential Drug-induced Liver Injury (DILI)

Signals of DILI post-Baseline II for the open label treatment period and post Baseline III for the open label treatment period with memantine will be assessed according to the FDA guideline¹, as well as by using additional criteria, as described below:

The number and percentage of patients post-Baseline II/Baseline III in the categories below for AST/ALT, and AST and ALT separately will be summarised:

Version: 1.0

- ULN < value ≤ 1.5 xULN
- $1.5xULN < value \le 2xULN$
- $2xULN < value \le 3xULN$
- $3xULN < value \le 5xULN$
- $5xULN < value \le 10xULN$
- $10xULN < value \le 20xULN$

LU Study Number: 14861B Trial Site Number: Study Level Pluto ID: CLI 00933680

Status: Final

• 20xULN < value

The number and percentage of patients post-Baseline II/Baseline III in the categories below for ALP and Bilirubin will be summarised:

- ULN<value ≤1.5xULN
- 1.5xULN< value <2xULN
- 2xULN< value ≤3xULN
- value >3xULN

In the summaries, each patient should be counted only once using the worst post-Baseline II/Baseline III assessment.

The cumulative number and percentage of patients post-baseline in the categories will also be summarised for each treatment period.

Number and percentage of patients fulfilling the joint criteria below post-baseline II/Baseline III will be summarised:

- (PEAK AST OR PEAK ALT>3xULN) AND PEAK BILI>2xULN AND PEAK ALP>1.5xULN
- (PEAK AST OR PEAK ALT>3xULN) AND PEAK BILI>2xULN AND PEAK ALP<1.5xULN
- PEAK GGT>200 (IU/L) without (PEAK AST OR PEAK ALT OR PEAK ALP>2xULN)
- Number and percentage of patients with a post-Baseline II /Baseline III value ≥5% for Beosinophils/leukocytes (ESOLE) will be summarised.

Evaluation of potential Drug-Induced Serious Hepatotoxicity (eDISH) will also be done by plots. Scatter plots of peak ALT/AST versus peak BILI in the treatment period (note that this means that the peak ALT/AST and the peak BILI may not occur at the same assessment timepoint). The values will be normalised by the ULN (unit xULN) and the X and Y-axes will be on log scale. The plot will include a reference line for ALT/AST values >3xULN, and a reference line for BILI values>2xULN. Four quadrants are defined by the reference lines, where the right upper quadrant being the most specific indicator for a drug's potential for causing serious liver injury (Hy's law quadrant). The plot will include number of patients in each quadrant.

Subject line plots with values-by-time for ALT, AST, ALP, Bilirubin, eosinophils, and GGT (overlaid in the same plot) will be generated for patients with ALT/AST > 1xULN post-baseline II/Baseline III. The test values will be normalised by the ULN (unit xULN) and the Y-axis will be on log scale. The time will be days since Baseline II/Baseline III, and reference lines for the day of first-and last IMP intake in the treatment period will be included. All assessments will be included. If there is more than one assessment at the same time point for a test, the maximum value will be used. A corresponding plot will be generated for patients with ALT/AST > 3xULN post-baseline I in the lead-in study or the open-label treatment period, where values in the lead-in treatment period and the open-label treatment will be included.

Version: 1.0

LU Study Number: 14861B Trial Site Number: Study Level Pluto ID: CLI 00933680

Status: Final

Conditional correlations of values adjusted for patient average level (mean value for each patient within each treatment period subtracted from the subject values at each visit within the treatment period) of ALT, AST, ALP, and bilirubin versus eosinophils will be generated as tables and scatter plots for:

- All patients
- Patients with a post-baseline II/Baseline III value of ALT/AST>2xULN
- Patients with a post-baseline II/Baseline IIIvalue of ALT/AST>3xULN

Patients in the APTS with a post-Baseline II/Baseline III value of GGT, ALT, AST, ALP, bilirubin, >1xULN will be listed, and the listing will include all available ALT, AST, BILI, ALP, GGT, and EOSLE values, sorted by completion/withdrawal status, treatment group, site, subject number, assessment date and time.

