16.9.3 Analysis of Liver Tests

In addition to the standard summary of clinical safety laboratory tests, the incidences of

- ALT/AST > 1x, 1.5x, 2x, 3x, 5x, 10x, 20x ULN
- TBL > 1x, 1.5x, 2x ULN
- AP > 1.5x, 2x ULN
- ALT/AST > 3xULN and TBL > 2xULN
- ALT/AST > 3xULN and TBL > 2xULN and AP \leq 1.5xULN
- ALT/AST > 3xULN and (TBL > 2xULN or INR > 1.5xULN) and AP \leq 1.5xULN

will be produced.

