11.1.9 Adverse Events Leading to Withdrawal

All adverse events leading to withdrawal will be listed.

TEAEs leading to withdrawal will be summarised by preferred term. For the open label treatment period the summary will also be generated by SOC and preferred term.

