Plasma concentrations of idalopirdine and memantine will be summarised descriptively for the APTS2 in the open-label treatment period with memantine.

13 Health Economic Analyses

The health economic assessments conducted during the open-label treatment period (RUD Lite, EQ-5D-3L and Dependence scale) in the open-label will be summarised by lead-in study. For the open label treatment period, absolute scores, change from Baseline I scores, and change from Baseline II will be summarised by visit week. The summaries of absolute scores and change from Baseline I scores will include data from the lead-in study and the open-label treatment period.

For the open label treatment period with memantine, absolute score and change from Baseline III in MMSE total score will be summarised by visit week.

14 Interim Analyses

No interim analyses planned.

Page 23 of 48 Trial Site Number: Study Level

LU Study Number: 14861B Pluto ID: CLI_00933680 Status: Final

Version: 1.0

15 Sample Size Considerations

Open-label treatment period:

The study will include eligible patients who have completed Visit 7 (Completion Visit) of the lead-in studies. Assuming a completion rate of 85% and that approximately 85% of these are eligible and complete the extension study, this results in a total of approximately $(3x310 + 3x280) \times 85\% \times 85\% \approx 1280$ patients completing this study.

Open-label treatment period with memantine (sub-study):

With a sample size of n=100 the upper 1-sided 90% confidence limit for 0 to 10 AEs observed is:

Number of AEs observed	0	1	2	3	4	5	10
Upper 1-sided CI for AE incidence	2.3%	3.9%	5.3%	6.6%	7.9%	9.1%	15.0%

This is regarded as sufficient accuracy for evaluating safety and tolerability.

16 Data and Analysis Standards and Statistical Software

The data will be collected and analysed in accordance with the Lundbeck standards specified in Lundbeck SDTM, Version 3.1.2 or later, SADs, Version 5.1 or later, and TGML, Version 7.0 or later.

The statistical software used will be SAS®, Version 9.4 or later.

17 Changes to Analyses Specified in the Protocol

C-SSRS will be summarized as worst case per treatment period rather than worst case per visit. However, all C-SSRS results for the study will be listed for those patients that experience any suicidal ideation or behaviour.

18 Details on Data Handling

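### The SAP drops the protocol's joint liver row that includes INR and does not declare the change, so the protocol's only transaminase-plus-INR incidence is not produced

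*SAP*

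**What the plan says.** **Protocol 16.9.3 (Analysis of Liver Tests)** plans, on top of the standard laboratory summaries, three joint incidences:

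1. ALT/AST above 3xULN with total bilirubin above 2xULN.
2. The same, with ALP at or below 1.5xULN.
3. "ALT/AST > 3xULN and (TBL > 2xULN or INR > 1.5xULN"), with ALP at or below 1.5xULN.

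**SAP 11.3.3 (Evaluation of Potential DILI)** says that signals will be assessed against the FDA guideline "as well as by using additional criteria, as described below". The joint criteria that follow are:

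- ALT/AST above 3xULN, bilirubin above 2xULN, ALP above 1.5xULN.
- The same with low ALP: ("PEAK AST OR PEAK ALT>3xULN) AND PEAK BILI>2xULN AND PEAK ALP<1.5xULN".
- A GGT criterion: "PEAK GGT>200 (IU/L) without (PEAK AST OR PEAK ALT OR PEAK ALP>2xULN").
- Eosinophils at or above 5%. This is printed in the same list but is a single-test count.

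INR is also absent from the eDISH plot and the patient line plots. For the liver listing, the SAP says that "the listing will include all available ALT, AST, BILI, ALP, GGT, and EOSLE values", again without INR.

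**SAP section 17 (Changes to Analyses Specified in the Protocol)** declares one change: "C-SSRS will be summarized as worst case per treatment period rather than worst case per visit". It does not mention liver criteria.

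**The concern.** The protocol's third row gives INR the same standing as bilirubin as the second element of the joint criterion. The SAP keeps the bilirubin arm and drops the INR arm without comment.

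Long-term safety and tolerability is the primary objective (SAP 1.1), and liver tests are the area where the drug has a known finding. In the phase II Alzheimer's study, raised transaminases were the stated exception to good tolerability and accounted for nearly all of the difference in withdrawals due to adverse events (Protocol 1.1.3.3). The third row is the only planned incidence in either document that combines transaminases with INR. If the SAP is followed as written, that incidence does not appear in the report, and a reader of section 17 has no reason to look for it.

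**Working it through.** There is no sample size or power figure to reproduce. The check is one of logic.

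**Step 1: which profiles each row counts.** Take a patient with peak ALT or AST above 3xULN. Let B = bilirubin above 2xULN, I = INR above 1.5xULN, A = ALP above 1.5xULN. That gives 2 x 2 x 2 = 8 profiles. The SAP's low-ALP row is read here as at or below 1.5xULN, to match the protocol.

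| Row | Condition | Profiles (of 8) |
|---|---|---|
| Protocol row 1 | B | 4 |
| Protocol row 2 | B and not A | 2 |
| Protocol row 3 | (B or I) and not A | 3 |
| SAP criterion 1 | B and A | 2 |
| SAP criterion 2 | B and not A | 2 |
| SAP GGT criterion | requires AST and ALT at or below 2xULN | 0 |

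**Step 2: what can be recovered.**

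- Protocol row 1 = SAP criterion 1 + SAP criterion 2 (2 + 2 = 4). Recoverable.
- Protocol row 2 = SAP criterion 2 (2 = 2). Recoverable.
- Protocol row 3 has 3 profiles and SAP criterion 2 covers 2 of them. The remaining one (not B, I, not A) is in no SAP joint criterion. The GGT row cannot catch it, because a value above 3xULN is also above 2xULN. Not recoverable.

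So two of the three protocol joint rows survive and one does not.

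**Step 3: does another output supply the missing count?**

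- *ALT/AST categories, eDISH plot, line plots, liver listing (SAP 11.3.3).* The patient appears in these, but without INR.
- *By-visit laboratory summaries (SAP 11.2).* "Descriptive statistics for the safety variables in the open label treatment period" would include INR, with its maximum (SAP section 5), but not joined to ALT/AST.
- *PCS flag (SAP Appendix IV, Table 1).* INR is flagged at 2.0 or above, as a single test. The protocol threshold of 1.5 x ULN is lower than 2.0 whenever the INR ULN is below 2.0/1.5 = 1.33. The documents do not give that ULN. For assumed values of 1.0, 1.1 and 1.2 the protocol threshold is 1.50, 1.65 and 1.80, so INR values from there up to 2.0 would meet the protocol row without raising a PCS flag.
- *Adverse events and withdrawals.* A clinically significant INR must be recorded as an adverse event (Protocol 9.4.2), and "All adverse events leading to withdrawal will be listed". These routes give individual cases, not an incidence under the protocol's definition.

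**The case against.** The strongest reply has four parts.

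**The FDA guideline reference may already cover INR.** The reference to criteria described below may attach only to the additional criteria, and Protocol 5.4 marks its own transaminase-plus-INR withdrawal criterion as following the same guidance. That link is real. But the SAP sentence specifies no INR output, and none of the criteria listed after it uses INR. A programmer working from section 11.3.3 would not produce the row.

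**These patients can be traced.** Protocol 5.4 requires withdrawal for ALT/AST above 3 times the upper limit with INR more than 1.5, so patients with concurrent values of that kind should appear in the withdrawal listing. Patients with INR of 2.0 or above get a listing of all their INR values (SAP 11.2), which can be matched to the liver listing. This stands as a limit on the consequence. It still gives no count, the recorded withdrawal reason need not name INR, and INR values between the protocol threshold and 2.0 trigger no INR listing.

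**The missing row is bounded.** It lies between SAP criterion 2 and criterion 2 plus the number in the eDISH quadrant with ALT/AST above 3xULN and bilirubin not above 2xULN. If that quadrant is empty, nothing is lost. This is correct, but a bound is not the committed incidence.

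**It is a descriptive study and the count may be zero.** Also true, and no patient number is claimed here. Zero under a stated definition is itself a result, and the SAP as written does not produce it. Protocol 16.12 has the SAP describe the planned analyses in more detail. A SAP may depart from the protocol, but section 17 is where it says so.

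**Conclusion.** The concern holds. The SAP has no counterpart to the third joint row of Protocol 16.9.3, section 17 does not declare the omission, and patients who would qualify through INR alone, with ALP at or below 1.5xULN, are counted in no joint liver criterion. One of three protocol joint rows is lost.

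The number of patients affected cannot be computed from the documents. The result rests on the listed criteria being complete. The comparison with the PCS flag also rests on an assumed INR ULN.

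This should be corrected, but it is a reporting gap and not a sign of harm. The clinical data described report no INR signal, and the phase II Alzheimer's study showed no group difference in bilirubin above ULN. Protocol 1.1.2 does report longer clotting time in rats at high exposure, and haemorrhages are an adverse event of special interest (SAP 11.1.11). Neither shows a clinical INR effect, but both make the row worth keeping.

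**What to change.** Add one row to the joint criteria in SAP 11.3.3, in the SAP's peak-value format and at the protocol's analysis threshold: (peak AST or peak ALT >3xULN) and (peak bilirubin >2xULN or peak INR >1.5xULN) and peak ALP <=1.5xULN. Protocol 16.9.3 does not say whether the values must be simultaneous. Peak values follow the convention of the other SAP rows, and the text should say so. If the omission was intended, declare and justify it in section 17 instead.

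Optional, in the same edit:

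- Add INR to the liver listing so that the new row can be traced to patients.
- Make the ALP split exhaustive (<=1.5xULN and >1.5xULN). As printed, a value of exactly 1.5xULN falls in neither row, though this may be an artefact of text extraction.

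Separately, Protocol 5.4 states the INR limit as a plain 1.5 and Protocol 16.9.3 as 1.5xULN. The sponsor should reconcile the two; this review does not say which is right.

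The cost is one table row per treatment period, or one sentence in section 17. INR is already collected (Protocol 9.4.2, Panel 5, under Coagulation). Compared with SAP criterion 2 with its ALP limit read as <=1.5xULN, the count in the restored row can only be equal or higher.
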